7.12.1 Reporting Procedures – Investigator notifying the IRB

Federal regulations require timely reporting by investigators to their local IRB of unanticipated problems posing risks to subjects or others. The following describes the NYULMC IRB reporting requirements.

Report promptly, but no later than 5 working days:

Researchers are required to submit reports of the following problems promptly but no later than 5 working days from the time the investigator becomes aware of the event:

- ***Unanticipated problems including adverse events that are unexpected and related***
 - *Unexpected: An event is “unexpected” when its specificity and severity are not accurately reflected in the protocol-related documents, such as the IRB-approved research protocol, any applicable investigator brochure, and the current IRB-approved informed consent document and other relevant sources of information, such as product labeling and package inserts.*
 - *Related to the research procedures: An event is related to the research procedures if in the opinion of the principal investigator or sponsor, the event was more likely than not to be caused by the research procedures.*
 - *Harmful: either caused harm to subjects or others, or placed them at increased risk*

Other Reportable events:

The following events also require prompt reporting to the IRB, though **no later than 5 working days:**

- **Complaint of a research subject** when the complaint indicates unexpected risks, or the complaint cannot be resolved by the research team.
- **Protocol deviations or violations** (includes intentional and accidental/unintentional deviations from the IRB approved protocol) for any of the following situations:
 - *one or more participants were placed at increased risk of harm*
 - *the event has the potential to occur again*
 - *the deviation was necessary to protect a subject from immediate harm*
- **Breach of confidentiality**
- **Incarceration of a participant** when the research was not previously approved under Subpart C and the investigator believes it is in the best interest of the subject to remain on the study.
- **New Information indicating a change to the risks or potential benefits** of the research, in terms of severity or frequency. (e.g. analysis indicates lower-than-expected response rate or a more severe or frequent side effect; Other research finds arm of study has no therapeutic value; FDA labeling change or withdrawal from market)

Reporting Process

The reportable events noted above will be reported to the IRB using the form: "Reportable Event Form" or as a written report of the event (including a description of the event with information regarding its fulfillment of the above criteria, follow-up/resolution and need for revision to consent form and/or other study documentation).

Copies of each report and documentation of IRB notification and receipt will be kept in the study's regulatory binder.

7.13 Serious Adverse Event Reporting

Any AE considered serious by the PI which meets the definition of an SAE included in Section 8.1.2, Definition of Serious Adverse Event will be submitted on an SAE form to the DCC. The DSMB will receive real-time notification of all SAEs.

We do not believe that this study requires FDA approval (IDE) because the sonication parameters that we are using fall well within the FDA ETC safety guidelines. However, if an IDE is required, we will report any adverse events within 10 calendar days if the information meets the following criteria:

- (A) A single occurrence of an event that is uncommon and known to be strongly associated with drug exposure (e.g., angioedema, hepatic injury, Stevens-Johnson Syndrome);
- (B) One or more occurrences of an event that is not commonly associated with drug exposure, but is otherwise uncommon in the population exposed to the drug (e.g., tendon rupture);
- (C) An aggregate analysis of specific events observed in a clinical trial (such as known consequences of the underlying disease or condition under investigation or other events that commonly occur in the study population independent of drug therapy) that indicates those events occur more frequently in the drug treatment group than in a concurrent or historical control group."

In addition, if the study requires an IDE, we will notify the FDA of any unexpected fatal or life-threatening suspected adverse reaction as soon as possible but in no case later than 7 calendar days of occurrence

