Number of participants	12 completers with a single session of PLIFUS and sham. Potentially, 4 additional participants will be enrolled if a single session of PLIFUS does not reduce functional connectivity or symptoms in the first 12 completers with good quality imaging data compared to sham, to assess whether 3 sessions of PLIFUS administered over 5 days reduces functional connectivity and symptoms.
Description of Study Agent/Procedure	The Sonicator-1000 system was developed in-house at the NYU Langone Health Tech4Health Institute. It is an MRI-guided neuronavigation single-element focused ultrasound platform, which has been modified from an earlier design that is currently being used in human research at Brigham and Women's Hospital. The system will non-invasively deliver ultrasound sonifications transcranially that selectively target specific areas of the brain using a neuronavigation system and the subject's MRI brain scan. The device is hardwired to only emit ultrasound power levels that are much-below levels that might produce damaging effects to the brain like tissue heating, cavitation, or blood-brain barrier disruption. Extensive research has been conducted to determine non-thermal pulse parameters and acoustic intensity levels to safely transmit PLIFUS through the scalp-skull-meninges media while localizing the low ultrasound energy into the brain for inducing neuromodulation. This has also been validated through preclinical and clinical studies using histological methods. The sonication parameters follow FDA and Electrotechnical Technical Commission regulation standards for diagnostic and therapeutic ultrasound. Previous human studies with similar laboratory-built custom PLIFUS devices have safely induced temporary neuromodulation in healthy subjects with no serious adverse effects following a single session of sonication.
Reference Therapy	Sham PLIFUS (noise and patient experience are identical)
Key Procedures	PLIFUS

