stimulation (TMS) and transcranial direct current stimulation (tDCS) which have a long-standing history of being safe for neuromodulation in humans.

Ultrasound for neuromodulation generally adheres to the safety guidelines of the Food and Drug Administration (FDA) for adult cephalic and obstetric diagnostic ultrasound applications ²⁸. These guidelines include derated limits of spatial peak pulse average intensity (I_{sppa}) of 190 W/cm², a spatial peak temporal average intensity (I_{spta}) of 720 mW/cm² (94 mW/cm² for adult cephalic), and a mechanical index of 1.9. Mechanical index is an indication of the ability to produce cavitation and related effects, therefore it has utility in predicting potential micromechanical damage ¹⁵. There are no specific guidelines for energy deposition into the human brain, but many of the mentioned studies follow the IEC 60601 part 2 standard for therapeutic equipment, which sets the limit on acoustic intensity at $I_{spta} = 3.0$ W/cm² ²⁹.

Past studies have determined the spatial error with neuronavigation-guided single-element piezoelectric transducers without skull aberration correction using bench-top testing and in preclinical studies was less than a 3 mm error in all directions when entering through side of the human skull ³⁰. Because the FUS will be entering through the flat acoustic temporal window to engage the Gpi in this study, we estimate minimal FUS beam distortion and the acoustic intensity will be attenuated by approximately 50%. Transmitting FUS through the top or back of the head has been shown to create larger shifts in beam direction, defocused beam focal dimensions, and significantly attenuated beam ultrasound pressure after the FUS beam passes through the skull and arrives at the brain target. Contours in the skull curvature and non-homogenous thickness produce these beam distortions and high attenuation effects which will be minimized in the proposed study. A particular benefit of FUS neuromodulation is its reversibility; any off-target effects are expected to diminish over time. Effects induced beyond the beam focus have been negligible in animal and human studies.

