We will use the ultrasound pulse parameters used by Cain et al ³⁹ for sonication of the globus pallidus (see previous paragraph) because their experiment demonstrated hemodynamic effects without adverse effects in healthy subjects and the stimulation parameters were very low-intensity and extremely low risk. If we do not see effects on functional connectivity or symptoms after the first 5 participants and if the single sessions are well-tolerated, we will switch to repeated dosing, applying three PLIFUS or sham sonifications over 5 days since repeated exposures may be required to produce detectable effects. A single session of PLIUS will include 5 minutes net total dosage of PLIFUS. The exposure uses ten 30 sec blocks of PLIFUS sonication with 30 sec rests in-between spread over ten minutes. Sonication will be delivered (Fig. 3) in low-amplitude pulses using a carrier wave frequency: 361 kHz, pulse repetition frequency: 100 Hz, and duty cycle: 5 % yielding an I_{spta} 1.5 W/cm² at the Gpi. The acoustic intensity used is in the range of FDA and Electrotechnical Technical Commission (ETC) regulation standards for diagnostic and therapeutic ultrasound, respectively ²⁸.

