2.2 Name and Description of the Investigational Agent

A detailed description of the device and its related procedures (photos, diagrams, and maintenance protocols) can be found in the DEVICE MANUAL document included in the IRB protocol packet. The Sonicator-1000 system was developed in-house at the NYU Langone Health Tech4Health Institute. It is a neuro-navigated single-element pulsed focused ultrasound platform. The system non-invasively delivers ultrasound sonifications intracranially that selectively target specific areas of the brain. The device is hardwired to only emit ultrasound power levels that do not yield damaging effects to the brain like tissue heating, cavitation, and blood-brain barrier disruption, in order to

ensure safe preservation of tissue integrity. Extensive research has been conducted to determine non-thermal pulse parameters and acoustic intensity levels to safely transmit PLIFUS through the scalp–skull–meninges media while localizing the low ultrasound energy into the brain for inducing neuromodulation. This has also been validated through preclinical and clinical studies using histological methods. The device acoustic output limits follow FDA ETC regulation standards for diagnostic and therapeutic ultrasound ²⁸. Previous human studies with similar laboratory built custom PLIFUS devices have safely induced temporary neuromodulation in healthy subjects with no adverse effects following a single session of sonication.

This type of device has been implemented in several PLIFUS neuromodulation studies with healthy human and neurological disease based studies. Most systems were fabricated and designed in a university institutional lab. No FDA-approved and commercial neuro-navigated single-element pulsed focused ultrasound device platform is available on the market. The Sonicator-1000 neuronavigation system uses the 3Dslicer OpenIGTLink and Plus Toolkit standard network communication protocol used for image-guided interventions. Plus Toolkit and 3Dslicer interface a stereoscopic optical tracking camera (Polaris Spectra or Vicra, Northern Digital, Inc) used to track in real-time the spatial locations of objects (E.g. FUS transducer, patient's head location, navigation stylus, and ultrasound calibration components) within 0.5 mm.

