2.2.3 Dose Rationale

The PLIFUS dose (sonication parameters) was selected based on the study by Cain et al³⁸ in which the Gpi was the target of sonication and produced changes in hemodynamics (MRI BOLD) without adverse effects. This method involves a very brief (10 minute) pulsed sequence that delivers relatively low energy, which is much lower than most previous transcranial studies and follow FDA and ETC regulation standards for diagnostic and therapeutic ultrasound. An $I_{SPTA} = 1.5 \text{ W/cm}^2$ is chosen as a conservative acoustic intensity compared to other FUS single-element device neuromodulation studies, where some studies reached up to $I_{SPTA} = 4.4 \text{ W/cm}^2$ at the brain target yielding no adverse effects¹⁸.

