2.4 Potential Risks & Benefits

2.4.1 Known Potential Risks

Risks of PLIFUS:

Because ultrasound has been used extensively for many years as a diagnostic tool in other fields of medicine, FDA safety regulations are well-established and well-validated. Some investigations of brain sonication have exceeded these safety guidelines and have not produced serious adverse effects. Theoretical adverse effects at very high levels of energy, far in excess of what will be used in this trial, include injury to brain tissue (lesions, bleeding, disruption of the blood-brain barrier) due to excessive heating or cavitation. In 704 human subjects who have been studied in 35 trials of transcranial ultrasound, no serious adverse events have been reported. Mild and transient side effects have been reported in 3.3% of subjects, including headache, neck stiffness, worsening mood, scalp heating, muscle twitches, cognitive effects (impaired attention), itchiness, sleepiness and anxiety⁴³. Rates of side effects associated with sham sonication have not been reported. The sonication parameters that will be employed adhere to FDA and ETC regulation standards for diagnostic and therapeutic ultrasound²⁸.

While PLIFUS is associated with only mild and transient side effects in healthy participants, it has not previously been studied in schizophrenia. It is possible that sonication of the Gpi might worsen symptoms of schizophrenia. If this happens, we expect it to be a transient effect, consistent with other behavioral effects. To minimize this risk, we will exclude from study individuals with a history of violence, aggression or suicidal behavior. We will be monitoring the severity of psychotic symptoms during sonication and will stop the procedure if symptoms worsen by more than 50% on AHRS and DESA or if the participant expresses clinically significant psychological distress or suicidal ideation. The study psychiatrist will remain with the participant during sonication and for 1 hour after completion of sonication to assess for worsening of psychosis and suicidality. The study psychiatrist will arrange for appropriate monitoring and further assessment after 1 hour if needed based on clinical judgement.

Risks of MRI:

A total of 7 MRIs will be performed using a Siemens 3T Prisma; one prior to the intervention visits and one preceding

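### The protocol says its ultrasound dose meets FDA limits, but the planned Ispta of 1.5 W/cm² is 2.1 and 16 times the FDA Ispta figures it quotes (720 and 94 mW/cm²)

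*Combined protocol and SAP*

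**What the plan says.** Section 2.1.2 lists derated FDA limits on three quantities: pulse-average intensity (Isppa) 190 W/cm², mechanical index 1.9, and temporal-average intensity (Ispta "720 mW/cm² (94 mW/cm² for adult cephalic"). It separately gives a therapeutic-equipment limit of Ispta 3.0 W/cm² under IEC 60601 part 2.

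The planned dose in section 2.1.4 is an Ispta of "1.5 W/cm² at the Gpi". Section 2.2.3 repeats the figure. Section 6.1.5 adds that it applies after the skull, with 50% attenuation estimated for all subjects.

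Compliance is asserted in seven places:

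- Protocol Summary, description of the study agent: "The sonication parameters follow FDA and Electrotechnical Technical Commission regulation standards for diagnostic and therapeutic ultrasound"
- Section 2.1.4: "The acoustic intensity used is in the range of FDA and Electrotechnical Technical Commission (ETC) regulation standards for diagnostic and therapeutic ultrasound, respectively"
- Section 2.2: "The device acoustic output limits follow FDA ETC regulation standards for diagnostic and therapeutic ultrasound"
- Section 2.2.3: the method is said to "follow FDA and ETC regulation standards for diagnostic and therapeutic ultrasound"
- Section 2.4.1 (risks): "The sonication parameters that will be employed adhere to FDA and ETC regulation standards for diagnostic and therapeutic ultrasound"
- Section 6.1: the parameters are said to be inside the FDA and ETC standards, as a reason for not needing an IDE
- Section 7.13: again as the reason no IDE is needed, "because the sonication parameters that we are using fall well within the FDA ETC safety guidelines"

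**The concern.** The planned Ispta is higher than both FDA Ispta figures the protocol quotes, and nowhere does the protocol say so. Section 2.4.1 remarks that some other investigations went beyond the FDA guidelines, which leaves the reader to infer that this one does not.

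The statement matters because of where it is used. In sections 6.1 and 7.13 it is a reason for the device-status position. In section 2.4.1 it is part of the risk description, for a population in which the protocol says the technique has not been studied.

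A related point cannot be settled from the documents. Section 2.1.3 says the earlier globus pallidus study in healthy volunteers stayed well under the FDA cranial threshold, and section 2.1.4 adopts that study's pulse parameters. That study's intensity is never given. The citation for it in section 2.1.4 is reference 39, which the list shows as a cognitive-remediation drug study; section 2.2.3 cites reference 38. If the earlier study used a lower intensity, its lack of adverse events does not cover this dose.

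**Working it through.** **Inputs.** Planned Ispta 1.5 W/cm² at the target (2.1.4, 2.2.3, 6.1.5); skull loss 50% (6.1.5); pulse repetition frequency 100 Hz and pulse width 0.5 ms (6.1.5); ten 30 s blocks with 30 s rests over 10 minutes (2.1.4); carrier frequency 361 kHz (2.1.4); limits from 2.1.2.

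**The protocol's own figures reproduce.** Duty cycle = 100 Hz × 0.5 ms = 5%. Net exposure = 10 × 30 s = 5 min. Both match the text.

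**Ispta against the quoted limits.** Ratio = planned Ispta / limit.

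| Reading of the planned dose | Ispta (mW/cm²) | ÷ 720 | ÷ 94 | ÷ 3000 |
|---|---|---|---|---|
| At target, as specified | 1500 | 2.08 | 15.96 | 0.50 |
| At target, averaged over rests (× 0.5) | 750 | 1.04 | 7.98 | 0.25 |
| Before the skull (÷ 0.5) | 3000 | 4.17 | 31.9 | 1.00 |

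**Isppa.** Isppa = Ispta / duty cycle = 1.5 / 0.05 = 30 W/cm² at the target and 60 W/cm² before the skull. Both are below 190.

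**Sensitivity to skull loss.** The output before the skull implied by the plan is 1.5 / (1 − 0.5) = 3.0 W/cm². Holding that fixed, Ispta at the target = 3.0 × (1 − a). The range for a is an assumption; the documents give only 50%.

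- a = 30%: 2.1 W/cm², which is 2.9 times 720 and 22 times 94.
- a = 70%: 0.9 W/cm², which is 1.25 times 720 and 9.6 times 94.
- a = 70% and averaged over rests: 0.45 W/cm², which is 0.45/0.72 = 0.63 times 720 (met) and 0.45/0.094 = 4.8 times 94.
- Loss needed to meet 720: 1 − 0.72/3.0 = 76%, or 1 − 0.72/1.5 = 52% if averaged over rests.
- Loss needed to meet 94: 1 − 0.094/3.0 = 96.9%, or 1 − 0.094/1.5 = 93.7% if averaged over rests.

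**Definitional mismatch.** The FDA figures are derated and the planned figure is an after-skull estimate, so they may not be strictly like for like. To restore compliance, the difference in definition would have to cut the planned value by 1 − 720/1500 = 52%, or by 1 − 94/1500 = 94%.

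**Mechanical index.** The protocol gives neither a value nor a pressure. Assume a plane wave and an acoustic impedance of 1.5 to 1.6 MRayl (neither is in the documents). Peak pressure is then √(2 × impedance × Isppa), and the index is pressure in MPa / √0.361. This gives 1.58 to 1.63 at the target, under 1.9, and 2.23 to 2.31 before the skull. Compliance on this limit depends on where it is evaluated, which is a reason to state it.

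**The case against.** The best defence is that the protocol's joint FDA and ETC label refers in practice to the 3.0 W/cm² therapeutic limit, which the target dose meets. Section 2.1.2 says there is no specific guideline for energy deposition in the brain, and that neuromodulation only generally follows the FDA diagnostic limits. But section 2.1.4 pairs FDA with diagnostic and ETC with therapeutic, one to one, so two separate standards are claimed and the FDA one fails on Ispta. Reading the claim as one about device output does not help either: the implied value before the skull equals 3.0 W/cm², with no margin.

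A second defence is that the excess over 720 depends on convention. This stands. Averaged over the rests it is 4%, and it disappears at 52% skull loss against an estimate of 50%. The 94 figure is exceeded under every reading tried, and even the 4% excess cannot support the section 7.13 wording.

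Third, every number is disclosed, so this is loose wording rather than concealment, and the wider safety case does not depend on it: 704 subjects in 35 trials without a serious event (2.4.1), and up to 4.4 W/cm² in other work without adverse effects (2.2.3). Section 6.1 also cites earlier human use and a separate non-significant-risk assessment, and offers to contact the FDA if the IRB asks. All of this stands and limits the consequence. The risk assessment and device manual were not available and may already hold the correct comparison. The protocol text would still need to agree with them.

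**Conclusion.** The concern holds. For FDA Ispta, the compliance statements contradict the limits quoted in section 2.1.2, by 2.1 times (720 mW/cm²) and 16 times (94 mW/cm²) at the dose as specified. The comparison with 94 is robust to averaging and to any plausible skull loss. The comparison with 720 is less so, because averaging over rests brings it close to equality. All values at the target rest on a 50% skull loss applied to every participant and on treating the derated limits as comparable with an after-skull estimate.

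Isppa is met, and the therapeutic limit is met at the target at any skull loss if the output is fixed at the implied 3.0 W/cm²; only its two-fold margin depends on the 50%. Whether the mechanical index limit is met cannot be determined from the protocol. Nothing here shows that the dose is harmful, which intensity is right, or that passing the FDA Ispta figures by itself requires an IDE. No estimate or test in the trial is affected. It should be fixed because a stated reason for the device-status position, repeated in the risk section, is wrong as written.

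**What to change.** In the Protocol Summary and sections 2.1.4, 2.2, 2.2.3, 2.4.1, 6.1 and 7.13, replace the general compliance wording with a comparison for each limit:

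- FDA Ispta: exceeded, 2.1 times 720 and 16 times 94 mW/cm² (1.04 and 8.0 times if averaged over rests).
- FDA Isppa: met, 30 against 190 W/cm².
- Therapeutic Ispta: met at the target, 1.5 against 3.0 W/cm²; say where the limit applies, since the implied value before the skull is 3.0.
- Mechanical index: give the value, the location and the assumptions.

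Say that these values assume 50% skull loss for all subjects. Make sure the non-significant-risk assessment and any IDE submission carry the same comparison, so that the IRB decides on that basis. State the Ispta used in the earlier globus pallidus study and correct its citation in section 2.1.4. If its intensity was lower, stop citing its lack of adverse events as covering this dose.

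The cost is a text amendment and IRB review. Dose, sample size, endpoints and data collection do not change. The statement becomes less favourable, and the IRB may ask for the FDA contact that section 6.1 already offers.
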